2.6. Time and Events Schedule

The flow chart showing trial phases and timing of treatment and assessments is given in [Table 1](#).

Table 1: Time and Events Schedule

Phase	Screening	Open-Label Treatment ^a						End-of-Study/Early Withdrawal	Follow-up Telephone Contact
		Baseline/ W1	M1	M2	M3	M6	M9		
Week(W)/Month(M)									
Study Day	≤-28	1 ^c	30	60	90	180	270	360	390 ^d
Study Day Window	-7days	±7days	±7days	±7days	±7days	±7days	±7days	±7days	±7days
Visit ^e	1	2	3	4	5	6	7	8	NA
Screening/Administrative									
Informed consent and assent	X								
Inclusion/exclusion criteria	X	X							
Medical/seizure history	X	X							
Physical activity evaluation ^f	X								
Prestudy AED and other therapy ^g	X								
Randomization		X							
Study Drug									
Dispense study drug		X	X	X	X	X	X		
Study drug accountability			X	X	X	X	X	X	
Pharmacokinetics									
Blood sample collection for quantitation of study drug ^h			X		X	X		X	
Safety									
Physical examination	X	X	X		X	X	X	X	
Neurologic examination	X	X	X		X	X	X	X	
12-lead ECG	X								
Height/weight ⁱ	X	X	X		X	X	X	X	
Vital signs (temperature, HR, RR, BP) ^j	X	X	X		X	X	X	X	
Clinical laboratory tests ^k	X		X		X	X	X	X	
Pregnancy test ^l	X	X	X	X	X	X	X	X	
24-hour urine collection ^m	X					X		X	
Tanner staging ⁿ		X				X		X	

CONFIDENTIAL – FOIA Exemptions Apply in U.S.

Table 1: Time and Events Schedule

Phase	Screening	Open-Label Treatment ^a						End-of-Study/Early Withdrawal	Follow-up Telephone Contact
		Baseline/ W1	M1	M2	M3	M6	M9		
Week(W)/Month(M)									
Study Day	≤-28	1 ^c	30	60	90	180	270	360	390 ^d
Study Day Window	-7days	±7days	±7days	±7days	±7days	±7days	±7days	±7days	±7days
Visit ^e	1	2	3	4	5	6	7	8	NA
Renal ultrasound	X					X		X	
Biochemical bone markers	X					X		X	
DEXA scan ^{b,q}		X				X		X	
Bone age x-ray		X						X	
Dispense seizure diary and take-		X	X	X	X	X	X		
Review seizure diary and take-			X	X	X	X	X	X	
Cogstate Battery ^r	X	X				X		X	
Animal Fluency Test NEPSY-II ^u	X	X				X		X	
Vineland Adaptive Behavior Scale ^v		X			X	X		X	
CBCL-Parent Version ^w		X			X	X		X	
C-SSRS ^x		X	X	X	X	X	X	X	
Ongoing Review									
Concomitant therapy	X	X	X	X	X	X	X	X	X
Adverse event monitoring	X	X	X	X	X	X	X	X	X

Footnotes appear on the following page.

^a Includes a titration period of approximately 6 to 8 weeks, followed by a maintenance period.

^b There may be an optional post-study follow-up phase to obtain DEXA measurements in a subgroup of subjects who experience a clinically important reduction (change in Z-score of -0.5 or greater) in BMD, based on local DEXA scan results, after 1 year of treatment with topiramate; these subjects will have a repeat DEXA scan 6 months after discontinuation of study drug.

^c The Day 1 visit will serve as the baseline visit. All procedures on Day 1 (except dispensing of study drug) should be completed before randomization.

^d The site will contact the subject via telephone at Month 13, to collect data on adverse events and concomitant medications.

^e Window for all visits will be ±7 days.

^f Adequacy of physical activity will be assessed with the Habitual Activity Estimation Scale.

^g Investigator will document inadequacy of any epilepsy treatment that the subject is receiving at the time of screening. Information regarding AED use and other medications within 2 years prior to the study will also be collected.

- ^h If possible, blood samples for determination of plasma topiramate and levetiracetam concentrations should be trough samples (taken immediately before the morning dose) and should coincide with samples drawn for clinical laboratory tests.
- ⁱ Subjects will be weighed in examination gowns or in lightweight clothing and without shoes. Height will be assessed using a wall-mounted stadiometer. All study site personnel measuring height will be blinded to treatment to avoid/minimize bias.
- ^j Orthostatic vital signs will be obtained for all subjects pending cooperation of subjects. A set of 3 measurements will be obtained at baseline only at intervals of 10 minutes. Thereafter, only 1 orthostatic vital sign measurement will be taken at all subsequent visits. The method for obtaining orthostatic vital signs will be as follows: subject will be supine for 5 minutes prior to measurement, and standing for 2 minutes prior to measurement.
- ^k Clinical laboratory tests (nonfasting) include serum chemistry, hematology, venous ammonia and urinalysis. Insulin-like growth factor 1, 1,25-dihydroxy-vitamin D, 25-hydroxy-vitamin D, and parathyroid hormone will be measured at screening and at Months 6 and 12/early withdrawal. The laboratory tests for 25-hydroxy-vitamin D, 1,25-dihydroxy-vitamin D, Parathyroid hormone (intact) and IGF-1 at screening will be evaluated centrally, but additional evaluation at a local laboratory is allowed in order to reduce the duration of the screening phase.
- ^l Serum pregnancy test at screening; urine pregnancy test at all other visits.
- ^m A 24-hour urine collection will be analyzed for pH, calcium, citrate, phosphorus, and creatinine levels. Collection instructions and storage conditions will be specified in the laboratory manual. A 14-day window on either side of the scheduled Month 6 visit will be allowed for 24-hour urine collection. The collection at Month 12 should be completed before the Month-12 visit as this evaluation should be obtained while the subject is still receiving study-drug therapy.
- ⁿ Tanner staging of subjects of age 8 years and above will be conducted by a qualified pediatric endocrinologist or by a physician trained in the method.
- ^o Renal ultrasound will be obtained under blinded conditions after randomization and will be read/interpreted centrally (local reading at the screening visit is acceptable to determine eligibility for randomization). Both the technicians administering the renal ultrasound scans and the local and central readers will be blinded to the study treatment group.
- ^p Biochemical bone markers will include serum calcium, phosphorus, parathyroid hormone [intact], 25-hydroxy-vitamin D, and 1,25-dihydroxy-vitamin D.
- ^q DEXA measurements will include posterior-anterior spine (lumbar) and total body less head areal BMD and BMC. Short-term precision testing will be performed for DEXA measurements according to standard protocols. The same DEXA machine will be used at each site for all subjects and all measurements; only clinical sites using recent-generation Hologic or General Electric Lunar systems will participate in the study; the GE/Lunar systems will only be used for subjects ≥ 5 years of age. If possible, the same technician should acquire all scans for any particular subject. Both the technicians administering the DEXA scans and the central reader will be blinded to the treatment group. For each time point, up to 3 scan attempts will be performed all on the same day (with repositioning between each scan), with the goal of obtaining 2 complete, movement-free scans of both the spine and whole body at screening.
- ^r A hand/wrist x-ray (in the nondominant hand/wrist) will be used to determine bone age.
- ^s Subjects will be given a take-home record, to capture data on study drug administration, concomitant medications, and items of general health, and a seizure diary with instructions to record seizure counts and the date and description of each seizure.
- ^t The computerized Cogstate Battery will be administered by non-expert (non-psychologist) study site personnel trained in the Cogstate administration method, with 2 practice sessions, 1 at screening and 1 at baseline prior to the baseline assessment. For subjects 6 to 15 years of age, the Detection Test, Identification Test, One Card Learning Test, One Back Test, and Groton Maze Learning Test will be administered. For cooperative subjects 4 to 5 years of age, the Detection Test and Identification Test will be administered.
- ^u The Animal Fluency Test NEPSY-II will be administered for subjects 6 to 15 years of age, with 1 practice session at screening.
- ^v The Vineland Adaptive Behavior Checklist will be completed by a parent or guardian for subjects 2 to 5 years of age.
- ^w The CBCL-Parent version will be used for all subjects. For subjects 2 to 5 years of age, the preschool version will be administered. For subjects 6 to 15 years of age, the school-age version will be administered.
- ^x The C-SSRS will be administered for subjects 6 to 15 years of age and will not be administered for subjects 2 to 5 years of age.

AED=antiepileptic drug; BMC=bone mineral content; BMD=bone mineral density; BP=blood pressure; CBCL=Child Behavior Checklist; C-SSRS=Columbia Suicide Severity Rating Scale; DEXA=dual energy x-ray absorptiometry; ECG=electrocardiogram; HR=heart rate; IGF-1=insulin-like growth factor 1; NEPSY =A Developmental NEUROPSYchological Assessment; RR=respiratory rate.

3. GENERAL ANALYSIS DEFINITIONS

Unless otherwise specified, all continuous endpoints (e.g., height, weight, BMD [observed and change from baseline values], etc.) will be summarized using descriptive statistics, which will include the number of subjects with a valid measurement (n), mean, SD, median, minimum, and maximum. Pharmacokinetics will be summarized using descriptive statistics including geometric mean and coefficient of variation (CV in percent will be defined as $CV(\%) = 100 * SD / \text{mean}$). All categorical endpoints (e.g., sex, adverse events, BMD Z-score decrease [>0.5 , >1.0 , >2.0], etc.) will be summarized using frequencies and percentages. In general, percentages will be calculated by dividing the number of subjects with the characteristic of interest by the number of subjects in the analysis population.

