3.3.3. Safety Analysis Set

This will include all randomized subjects who received at least 1 dose of study medication. This population will be used for all analyses, including any DMC analyses. All subjects will be analyzed according to treatment they received by first study drug dispensation.

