7.1. Kidney Stones

Percentage of subjects with kidney stones and other US findings suggestive of stones will be summarized by treatment group.

The renal ultrasound findings will also be presented in a listing.

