7.3. Height

Observed height values, change from baseline, Z-scores for height, change from baseline in Z-scores for height, height velocity at 1 year, and height velocity Z-score will be summarized by visit using descriptive statistics. Height, Z-scores for height, height velocity and height velocity Z-scores will be calculated as the mean of the three measurements. The number and percentage of subjects with a height Z-score decrease of >0.5 , >1.0 , and >2.0 will be listed and summarized by visit using descriptive statistics. MMRM analysis will also be performed for changes from baseline and changes in Z-Scores from baseline.

The change in height z-scores will also be summarized by subject's serum bicarbonate categories.

Height velocity values and associated Z-scores will be computed for each post-baseline year in the study, based on the methods described in [Appendix 6](#).

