7.4. Bone Mineral Density (BMD) and Bone Mineral Content (BMC)

DEXA measurements will include posterior-anterior spine and total body less head areal (TBLH) BMD and BMC. Observed BMD (spine and TBLH) and BMC (spine and TBLH) values change from baseline, Z-scores as well as height adjusted Z-scores for BMD and BMC, change from baseline in Z-scores and height adjusted Z-scores for BMD and BMC, and percent change from baseline in BMD and BMC will be summarized by visit using descriptive statistics. The number and percentage of subjects with a BMD Z-score and adjusted Z-score decrease of >0.5 , >1.0 , and >2.0 will be listed and summarized by visit using descriptive statistics. MMRM analysis will also be performed for changes from baseline, changes in Z-Scores from baseline, and changes in height adjusted Z-Scores from baseline.

Subjects with a clinically important reduction in BMD defined as change in Z-score and height adjusted Z-score of -0.5 or greater) at 6 months or 12 months, will have a repeat DEXA scan 6 months after discontinuation of study drug. These subjects will be summarized and listed in the DEXA table and listing.

The change in BMD z-scores will also be summarized by subject's serum bicarbonate categories.

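### The SAP's default denominator counts children with no value in a visit window as non-events in the by-visit height and BMD outlier percentages

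*SAP*

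**What the plan says.** SAP section 3 treats continuous and categorical endpoints differently. Continuous summaries report the number of children with a valid measurement. For categorical endpoints, among which it names the BMD Z-score decrease categories, the rule, introduced by a qualifier that marks it as a default, is that "percentages will be calculated by dividing the number of subjects with the characteristic of interest by the number of subjects in the analysis population".

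SAP 3.3.3 defines the safety analysis set, used for all analyses: "This will include all randomized subjects who received at least 1 dose of study medication". No post-baseline assessment is required.

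The endpoint sections do not replace the default:

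- SAP 7.3: "The number and percentage of subjects with a height Z-score decrease of" more than 0.5, 1.0 and 2.0, by visit.
- SAP 7.4: "The number and percentage of subjects with a BMD Z-score and adjusted Z-score decrease of" the same three cut-offs, by visit.
- SAP 7.1: "Percentage of subjects with kidney stones and other US findings suggestive of stones", by treatment group. No by-visit table is stated.

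**The concern.** A child without a height or DEXA value in a window contributes one to the denominator and can contribute nothing to the numerator. Missing data are thereby recorded as absence of harm. The protocol lists these outlier percentages and the stone percentage among its key safety endpoints, in a study done as a postmarketing safety requirement, so an error in this direction is the unwelcome one. If the arms differ in how many children are assessed, the arm with more missing data looks safer for that reason alone.

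**Working it through.** **1. The plan's own figures.** Protocol 11.2 and SAP 2.4 plan 141 per arm with 29% dropout; Protocol 11.2 gives 100 completed children per arm. 100 / (1 − 0.29) = 140.8, rounded up to 141 per arm, 282 in total. This matches.

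Protocol 11.2 gives a Wilson-score 95% CI width of 0.12 for stones, at 7% against near zero with 100 completed children per arm. The Wilson limits are 0.0343 to 0.1375 for 7/100 and 0 to 0.0370 for 0/100. Combining them for the difference:

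- lower: 0.07 − √((0.07 − 0.0343)² + 0.0370²) = 0.019
- upper: 0.07 + (0.1375 − 0.07) = 0.137
- width: 0.119, which rounds to 0.12

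The protocol's precision therefore rests on the 100 completers, not on all 141 randomized.

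**2. Effect of the SAP default.** Let r be the rate among assessed children and a the share of the safety set assessed in that window.

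Reported percentage = events / safety set = r × a

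**3. Do early-withdrawal assessments fill the gap?** Protocol 10.2 asks for end-of-study assessments when treatment stops early, but the SAP 3.1 windows decide where they count.

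- DEXA (Table 8): Month 6 is days 31 to 270; Month 12 starts on day 271.
- Height (Table 2): Month 9 is days 226 to 315; Month 12 starts on day 316.

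A child who stops and is assessed on day 200 has both values in Month 6 and none in Month 12. One assessed on day 280 has a Month 12 DEXA but a Month 9 height. Each remains in the Month 12 denominator for whatever is missing.

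**4. Size for height and BMD outliers at Month 12.** The share assessed is not given. The table assumes that every dropout lacks a Month 12 value and that r = 20%. The 29% is the planning value; 22% and 35% are the two earlier-study rates cited with it.

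| Not assessed | Factor a | 20% shows as |
|---|---|---|
| 22% | 0.78 | 15.6% |
| 29% | 0.71 | 14.2% |
| 35% | 0.65 | 13.0% |

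Check in counts: 20 events in 100 assessed, divided by 141, is 14.2%.

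**5. Unequal missingness.** With the same r in both arms, the false difference is r × (a₁ − a₂). For r = 20% and an assumed 10-point gap in the share assessed, 0.20 × 0.10 = 2 percentage points.

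**6. Stones.** Any post-baseline ultrasound can supply an event, so full dilution comes only from children with none. At 7% among those scanned, an assumed 5% unscanned gives 7% × 0.95 = 6.65%, and 10% gives 7% × 0.90 = 6.3%.

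**The case against.** The strongest reply is that the rule opens with a qualifier, so it is a default covering sex, adverse events and everything else, and a programmer could use the assessed children for by-visit tables. That is fair as to intent. But the qualifier only permits an exception, and none is written for these endpoints. The continuous summaries also show n by visit and outlier subjects are listed, so a careful reader could rebuild the rates. That limits the damage without making the tabulated percentage right.

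Several stronger readings are tempting, and the documents do not support them:

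- **That all outlier and stone rates are too low.** Dilution occurs only where values are missing. Early height visits may be barely affected.
- **That a 7% stone rate would be reported as 7/141 = 5.0%.** SAP 7.1 states no by-visit table, ultrasound is done at Month 6 and at Month 12 or early withdrawal, and Table 3 assigns any scan from day 2 to a window. A child who drops out can still be counted as a stone event, so 5.0% is a worst case.
- **That 29% dropout means 29% unassessed.** Under Protocol 10.1, a child who adds another AED and stays to Month 12 is a non-completer yet can have Month 12 data, and a DEXA at withdrawal from day 271 counts as Month 12.
- **That 35% and 22% describe the two arms.** They are the double-blind-phase and overall dropout rates of one earlier study. Nothing in the documents predicts an arm split.
- **That the planned confidence intervals will be too narrow.** Protocol 11.4 promises intervals for proportions, but the SAP specifies 95% CIs only for the mixed-model treatment differences.

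**Conclusion.** The point holds for the by-visit height and BMD outlier percentages: followed as written, the rule understates them relative to the rate among assessed children whenever values are missing. It holds more weakly for stones. The direction is certain; the size is not. The factors of 0.78 to 0.65 at Month 12 assume that no dropout has a Month 12 value, and the 20% outlier rate and the 5% and 10% unscanned shares are assumptions. SAP section 1 records that enrollment stopped early, so the planned 141 per arm is illustrative, but the factor depends on the share assessed and not on the number enrolled. This should be corrected before the tables are produced, because a stated rule gives a misleading safety rate and no exception to it is written.

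**What to change.** Add to SAP section 3, with a cross-reference from 7.1, 7.3 and 7.4:

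- By-visit height and BMD outlier percentages use children with both a baseline value and a value in that visit window.
- The stone percentage uses children with at least one post-baseline renal ultrasound or a clinically diagnosed stone. The second route keeps in a child withdrawn for a stone before any scan; show how many enter that way.
- Each table shows n/N and the number missing, by arm.

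The cost is SAP wording and table shells; no new data are needed. Reported percentages become somewhat higher and denominators vary by visit. The change does not remove bias if children who leave differ from those who stay, nor does it resolve partial follow-up for stones, which is why the number missing by arm belongs in the table.

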3.1. Visit Windows

The statistical analysis for safety will be based on time intervals that are constructed according to the number of days in trial from day 1. (See table 2-8)

The analysis windows for height, weight, exposure, vital signs, laboratory tests, physical examination and neurological examinations is given in [Table 2](#).

Table 2: Definition of windows for height, weight, exposure, vital signs, laboratory tests, physical examination and neurological examinations:

Scheduled Visit Number	Time Interval (label on output)	Time Interval (Day) ^a	Target Time Point
1,2	Baseline	-35 to 1	1
3	Month 1	2 to 60	30
5	Month 3	61 to 135	90
6	Month 6	136 to 225	180
7	Month 9	226 to 315	270
8	Month 12	≥ 316	360

^a The randomization day is Day 1.

The analysis windows for Renal Ultrasound, Cogstate, Tanner Staging and 24 hour urine collection is given in [Table 3](#).

Table 3: Definition of windows for Renal Ultrasound, Cogstate, Tanner Staging and 24 hour urine collection:

Scheduled Visit Number	Time Interval (label on output)	Time Interval (Day) ^a	Target Time Point
1, 2	Baseline	-35 to 1	1
6	Month 6	2 to 270	180
8	Month 12	≥ 271	360

^a The randomization day is Day 1.

The analysis windows for C-SSRS is given in [Table 4](#).

Table 4: Definition of windows for C-SSRS:

Scheduled Visit Number	Time Interval (label on output)	Time Interval (Day) ^a	Target Time Point
1, 2	Baseline	-35 to 1	1
3	Month 1	2 to 45	30
4	Month 2	46 to 75	60
5	Month 3	76 to 135	90
6	Month 6	136 to 225	180
7	Month 9	226 to 315	270
8	Month 12	>=316	360

^a The randomization day is Day 1.

The analysis windows for Vineland Scale and CBCL is given in [Table 5](#).

Table 5: Definition of windows for Vineland Scale and CBCL:

Scheduled Visit Number	Time Interval (label on output)	Time Interval (Day) ^a	Target Time Point
1, 2	Baseline	-35 to 1	1
5	Month 3	2 to 135	90
6	Month 6	136 to 270	180
8	Month 12	>=271	360

^a The randomization day is Day 1.

The analysis windows for Bone Age is given in [Table 6](#).

Table 6: Definition of windows for Bone age:

Scheduled Visit Number	Time Interval (label on output)	Time Interval (Day) ^a	Target Time Point
1	Baseline	-35 to 180	1
8	Month 12	>=181	360

^a The randomization day is Day 1.

The analysis windows for seizure count is given in [Table 7](#).

Table 7: Definition of windows for seizure count:

Scheduled Visit Number	Time Interval (label on output)	Time Interval (Day) ^a	Target Time Point
3	Month 1	2 to 45	30
4	Month 2	46 to 75	60
5	Month 3	76 to 135	90
6	Month 6	136 to 225	180
7	Month 9	226 to 315	270
8	Month 12	>=316	360

^a The randomization day is Day 1.

The analysis windows for DEXA is given in [Table 8](#).

Table 8: Definition of windows for DEXA:

Scheduled Visit Number	Time Interval (label on output)	Time Interval (Day) ^a	Target Time Point
1, 2	Baseline	-35 to 30	1
6	Month 6	31 to 270	180
8	Month 12	>=271	360

^a The randomization day is Day 1.

The analysis windows for Pharmacokinetics is given in [Table 9](#).

Table 9: Definition of windows for Pharmacokinetics

Scheduled Visit Number	Time Interval (label on output)	Time Interval (Day) ^a	Target Time Point
3	Month 1	2 to 45	30
5	Month 3	46 to 135	90
6	Month 6	136 to 270	180
8	Month 12	>=271	360

^a: The randomization day is Day 1

Baseline is defined as the last non-missing observation (including an unscheduled visit) prior to or equal to Day 1 (except for DEXA and Bone age, where baseline includes up to 30 days and 180 days post-baseline, respectively).

For post baseline observations, if more than one visit (including an unscheduled visit) occurs in the same time window, the visit nearest to the target day will be used in the analysis. In the case of an equal distance in time, the latest visit will be used.

Data that are not used in the analysis due to multiple observations or being excluded from the above defined time intervals will be displayed in the data listing.

